# 2.3 Study Design

This is an open-label Phase I study of 0.5% PRO 2000/5 Gel (P) to be conducted among 60 HIV-uninfected sexually active women from Pune, India. The male partners of these women also will be enrolled in the study. Half of the female participants will be at low risk for HIV infection; the other half will be at higher risk (see Sections 3.1.2 and 3.2.2 for definitions of low and higher risk). Both low and higher risk participants will apply 0.5% PRO 2000/5 Gel (P) twice daily for 14 consecutive days between menses, and agree to have vaginal intercourse with a single male partner, using study-provided male condoms, at least twice per week during the two weeks of product application.

After providing written informed consent, female participants will undergo eligibility screening, including medical history, pelvic exam, Pap smear (if there is no documented normal Pap in the past three months), urine pregnancy testing, HIV and STD counseling and testing, hematology and coagulation testing, and liver and renal function testing. For participants who are presumptively eligible at this visit, an Enrollment Visit will be scheduled to take place 2-7 days after the participant's next menstrual period, but within 30 days of initial screening. In addition, the participant's male sexual partner will be informed of the study and its requirements of him, asked to

provide written informed consent to take part, and be screened for eligibility. Female participants whose male partners are not willing to provide written informed consent, or are not found to be eligible, will not be eligible to take part in the study. Female participants in a previous microbicide study in Pune indicated that they would not participate without the knowledge of their male partners due to concerns over domestic violence.

At their Enrollment Visits, female participants will be provided their screening test results. Presumptively-eligible participants will undergo a pelvic exam with colposcopy, and urine pregnancy testing to confirm their eligibility. Hematology, coagulation, and liver and renal function testing will be performed, and plasma will be collected and stored for batch testing for PRO 2000/5 drug levels at the end of the study. In addition, participants will be provided with:

- Supplies of 0.5% PRO 2000/5 Gel (P), applicators, panty liners, and male condoms;

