# 3.1 Inclusion Criteria

# 3.1.1 All Female Participants

Women who meet all of the following criteria (by self-report, unless otherwise specified) are eligible for inclusion in this study:

- Age 18-45 years.
- Able and willing to provide written informed consent to take part in the study.
- HIV-uninfected by licensed enzyme immunoassay (EIA).
- Have a regular menstrual cycle with a minimum of 21 days between menses, or are amenorrheic due to long-acting progestin use.
- Have had no change in hormonal contraceptive use in the three months prior to screening and agree to continue use of their preferred contraceptive method while in the study, provided these methods are not listed below as exclusionary methods.
- Have a normal Pap smear at screening, or are able to document a normal Pap smear within three months prior to screening.
- Are sexually active with a single male sexual partner who is eligible for this study per Section 3.1.3 and 3.2.3 below.
- Agree to abstain from sexual intercourse beginning 48 hours prior to the Enrollment Visit.
- Able and willing to complete Daily Study Records.
- Agree for the duration of the study to:
  - > apply 0.5% PRO 2000/5 Gel (P) as required per protocol;
  - have vaginal intercourse only with the single male sexual partner who is eligible for this study per Section 3.1.3 and 3.2.3 below;
  - have vaginal intercourse at least two times per week while taking part in the study;
  - use study-provided condoms for each act of vaginal intercourse while taking part in the study;
  - > agree for the duration of the study to abstain from:
    - insertion of fingers and other objects into the vagina
    - receiving oral sex
    - receiving anal sex
    - using a female condom, diaphragm, or cervical cap
    - using any vaginal product other than 0.5% PRO 2000/5 Gel (P), including lubricants, desiccants, or feminine hygiene products
    - douching
    - participating in other vaginal microbicide or contraceptive studies while taking part in this study; and
    - using non-therapeutic intravenous drugs.

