#### 3.2 Exclusion Criteria

#### **3.2.1** All Female Participants

Women who meet any of the following criteria by self-report at screening or enrollment, unless otherwise specified, will be excluded from this study:

Note: Women with observed abnormalities as described below will be referred for appropriate clinical follow-up and/or treatment. Since all potential participants are eligible for India's national health service, further clinical care will be provided at no cost to the participant.

- Are menopausal.
- Are currently breastfeeding.
- Are currently using, or within the year prior to screening have used, non-therapeutic intravenous drugs.
- Are pregnant (based on a urine pregnancy test).
- Have one or more grade 3 or higher liver, renal, or hematology abnormalities, as defined by the Division of AIDS (DAIDS) Toxicity Tables at screening.
- Have a positive urine culture.
- Have a clinically detectable genital abnormality (i.e., vulvar, vaginal, cervical and/or perianal ulcer and/or lesion).
- Have a history of adverse reaction to anticoagulant(s).
- Have a history of sensitivity/allergy to latex.
- Have used any spermicide or spermicidally lubricated condom within the past week (prior to enrollment).
- Have participated in any other investigational drug trial within 30 days prior to screening .
- In the three months prior to screening have (any of the following):
  - used an intrauterine contraceptive device,
  - ▹ had an abnormal Pap smear,
  - ▹ been pregnant,
  - ➢ had gynecologic surgery,
  - ➢ had breakthrough menstrual bleeding, or
  - ➤ had vaginal bleeding during or following sexual intercourse.

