#### 6.0 Adverse Event Reporting Requirements

An AE is defined as any untoward medical occurrence in a clinical research participant administered an investigational product and which does not necessarily have a causal relational with the investigational product. As such, an AE can be an unfavorable or unintended sign (including an abnormal laboratory finding, for example), symptom or disease temporally associated with the use of an investigational product, whether or not considered related to the product.

Study participants will be provided a 24-hour telephone number and instructed to contact the study clinician to report any AEs they may experience, except for life-threatening events, for which they will be instructed to seek immediate emergency care. Depending on the severity of the event, the clinician will instruct the participant to present to the study site (for more mild events) or to an emergency room (for more serious events) for immediate evaluation. Where feasible and medically appropriate, participants will be encouraged to seek medical care where the study clinician is based, and to request that the clinician be paged or otherwise contacted upon their arrival. With appropriate permission of the participant, records from all non-study medical providers related to AEs will be obtained and required data elements will be recorded on study case report forms. All participants reporting an AE will be followed clinically, until the AE resolves (returns to baseline) or stabilizes.

Study site staff will document on study case report forms all AEs reported by or observed in enrolled study participants regardless of severity and presumed relationship to study product. All AEs will be defined as described in the DAIDS HPTN SAE Reporting Manual (dated June 1, 2001). All AEs will be graded using the DAIDS Table for Grading Severity of Adverse Experiences (also referred to as the "Toxicity Table"). Both the DAIDS SAE Reporting Manual and the Toxicity Table are provided in the studyspecific procedures manual. The investigator or designee will assess the relationship of all AEs to the study product based on the DAIDS HPTN SAE Reporting Manual, the Investigator's Brochure, and his/her clinical judgment.

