#### 7.4 Data Analysis

Statistical analyses, described in Sections 7.4.1 and 7.4.2, will be performed using the SAS® and StatXact statistical software packages. As noted above, all analyses will include available data on all 60 study participants. When the use of descriptive statistics is required, the following methods will be used: for categorical variables, the number and percent in each category, with exact confidence intervals for the proportions; for continuous variables, the mean, median, standard deviation, quartiles, and range (minimum, maximum). Changes from baseline to follow-up will be analyzed using McNemar's test (for categorical response variables) or the paired t-test (for continuous response variables. A summary of the analysis tables that will be created is provided in Appendix VIII.

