## **Appendix VIII: Analysis Tables**

- 1. Study completion number and percentage of subjects completing the study. Day of discontinuation.
- 2. Baseline demographics descriptive summaries of demographic characteristics.
- 3. Pelvic exam at baseline descriptive summaries of pelvic exam variables at baseline.
- 4. Colposcopic exam at baseline descriptive summaries of colposcopic exam at baseline.
- 5. Laboratory measurements at baseline descriptive summaries of laboratory measurements.
- 6. Acceptability at baseline descriptive summaries of acceptability variables at baseline.
- 7. Adherence descriptive summaries of adherence.
- 8. Protocol deviations descriptive summaries of protocol deviations.
- 9. Pelvic exam at Day 2, Day 7, and Day 14 descriptive summaries of pelvic exam variables at Day 2, Day 7, and Day 14.
- 10. Change in selected pelvic exam variables from baseline to Day 2, Day 7 or Day 14 change from baseline to Day 2, Day 7, and Day 14 pelvic exam variables.
- 11. Colposcopic exam at Day 2 and Day 14 descriptive summaries of colposcopic exam at Day 2 and Day 14.
- 12. Change in selected colposcopic exam variables from baseline to Day 2 and Day 14 baseline, Day 2, and Day 14 colposcopic exam variables.
- 13. Treatment emergent adverse events number of subjects experiencing adverse events while on treatment by MeDRA SOC and preferred term. Summaries will be given by severity and by relationship to study treatment.
- 14. Change in selected AEs from baseline to Day 2, Day 7, and Day 14 number and percentage of subjects experiencing AEs at baseline and at Day 2, Day 7, and Day 14 follow-up visits.
- 15. Laboratory data at Day 14 descriptive summaries of laboratory measurements.

- 16. Change in laboratory data descriptive summaries of the change in laboratory measurements from baseline to Day 14.
- 17. Acceptability at Day 14 descriptive summaries of acceptability variables at and Day 14.
- 18. Change in acceptability variables from baseline to Day 14 baseline and Day 14 acceptability variables.
- 19. Concomitant medications descriptive summaries of concomitant medications at baseline, Day 2, Day 7, and Day 14.

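### For genital ulcers/lesions and for adverse events the baseline is zero by design, so McNemar's test of change from baseline cannot separate a gel effect from background

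*Protocol*

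**What the plan says.** Section 7.4 sets a general rule for categorical change: "Changes from baseline to follow-up will be analyzed using McNemar's test (for categorical response variables"). It adds that the analyses "will be performed using the SAS® and StatXact statistical software packages". It states no significance level and does not say whether the test is exact or asymptotic.

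Appendix VIII lists three tables of change from baseline to which the rule would apply: selected pelvic exam variables (item 10), selected colposcopic variables (item 12) and selected adverse events (item 14). Item 14 is described as "number and percentage of subjects experiencing AEs at baseline and at Day 2, Day 7, and Day 14 follow-up visits".

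Four other provisions bear on what baseline can look like:

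- **Exclusion, all women (3.2.1).** "Women who meet any of the following criteria by self-report at screening or enrollment, unless otherwise specified, will be excluded from this study". One criterion is: "Have a clinically detectable genital abnormality (i.e., vulvar, vaginal, cervical and/or perianal ulcer and/or lesion"). Section 2.3 uses the Day 0 pelvic exam with colposcopy to confirm eligibility, and the same exam is the baseline.
- **Low-risk women only (3.2.2).** A wider set of signs, including erythema, edema, petechiae and abrasions, bars a woman from the low-risk group. Asymptomatic BV and yeast colonization do not.
- **Abstinence (3.1.1).** "Agree to abstain from sexual intercourse beginning 48 hours prior to the Enrollment Visit". No such rule precedes the Day 2, 7 or 14 exams, while intercourse at least twice a week is required.
- **Adverse event definition (6.0).** "An AE is defined as any untoward medical occurrence in a clinical research participant administered an investigational product".

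On design, Section 2.3 says: "This is an open-label Phase I study of 0.5% PRO 2000/5 Gel (P) to be conducted among 60 HIV-uninfected sexually active women". There is one gel group and no inert comparator.

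**The concern.** McNemar's test compares women who change from absent to present with women who change from present to absent. Its null is that the two are equally likely. That null stands for no effect only if a woman can be positive at either time.

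A woman with a genital ulcer or lesion at Day 0 is not enrolled, and an adverse event cannot exist before the first dose. For these variables the second kind of change is impossible. The null is then false as soon as any new finding can occur, whatever its cause: intercourse, applicator or speculum contact, or a new infection. With no control arm, nothing in the trial estimates how often such findings would arise without active gel.

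Item 14 has a further problem whichever test is used. It counts adverse events at baseline, which Section 6 does not allow to exist.

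At stake is a p-value for worsening, in a safety study meant to inform a Phase II/III trial, that could be read as evidence of harm from the gel when it reflects selection at entry.

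**Working it through.** **The plan's own figures.** Section 7.2 tabulates the probability of two or more events among 60 women. The binomial tail gives 0.121, 0.808, 0.929, 0.986, 0.999 and 1.000 at true rates of 1, 5, 7, 10, 15 and 20%, which matches the table. The protocol gives no operating characteristic for McNemar's test.

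**Assumptions.** Two-sided 0.05; exact test (StatXact is named).

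**Step 1: findings needed for significance.** Let b be the women who improve and c those who worsen. With no baseline positives b = 0, and the exact two-sided p-value is 2 × 0.5^c.

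- c = 5: 2 × 0.03125 = 0.0625
- c = 6: 2 × 0.015625 = 0.03125

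Six new findings among 60 women (10%) suffice. The asymptotic test without continuity correction needs only four (chi-square = c = 4, above 3.84).

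**Step 2: how often an inert gel would reach this.** If all 60 women are clean at baseline and the finding has prevalence p at the tested visit from causes other than the gel, the probability is P(X ≥ 6), X ~ Binomial(60, p).

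| Background p | Where it comes from | P(X ≥ 6) |
|---|---|---|
| 4% | 1/25 cervical abrasion on placebo, abstinent women (1.2.2) | 0.03 |
| 5.5% | half of the 11% ulceration in the earlier sexually active study (1.2.2) | 0.11 |
| 8% | half of the 16% abrasion in that study | 0.35 |
| 10% | illustrative | 0.56 |

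Only the first row is an observed inert-gel rate. The halving in the next two rows is an assumption. It rests on the statement in 1.2.2 that half of the epithelial disruption findings were linked to possible applicator or speculum trauma, sexual activity or HSV. For comparison, the nominal error rate in the direction of worsening is 0.025.

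With the uncorrected asymptotic test, P(X ≥ 4) is 0.22 at 4% and 0.86 at 10%.

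**Step 3: only the low-risk half clean.** For signs that 3.2.2 filters but 3.2.1 does not name, take 30 women as clean at baseline. Give the other 30 the same prevalence p at baseline and follow-up, independently. The exact test then shows significant worsening with probability 0.01 at 4%, 0.06 at 8%, 0.09 at 10% and 0.18 at 16%. With no woman filtered it is 0.012 at 10%.

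**Step 4: adverse events.** Here all 60 women are at zero by definition, so Step 2 applies to any event type that is common for reasons other than the gel. Section 1.2.2 reports intermenstrual bleeding in all dose groups of the first trials, placebo included, but gives no rate for it on placebo.

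**The case against.** A reader might infer that an inert gel would show significant worsening across these tables. The document does not support that.

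- The background rate is unknown. At the only placebo lesion rate given, 4%, the exact test signals 3% of the time. The 5.5% and 8% rates come from women using 2% or 4% active gel, counted over the course of that study rather than at one visit, and the halving refers to findings rather than women. They probably lean high.
- A reader might also infer that every baseline variable is forced clean. Section 3.2.1 names ulcers and lesions; abrasion, erythema and edema are not clearly excluded in higher-risk women. The November 2003 letter deletes the wider list as redundant to 3.2.1, which suggests the team read 3.2.1 broadly, but the wording of 3.2.1 did not change. The 48-hour abstinence may lower findings due to intercourse at Day 0; it does not make them zero.
- No stated decision rests on these tests. The primary analysis tabulates endpoints, and the mucosal ones already set aside pathogen and mechanical trauma. Accrual suspension depends on related grade 3 or higher events.
- Items 10, 12 and 14 cover selected variables that the protocol does not name, and item 14 itself names no test.

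All of this limits the size and reach of the point. It does not restore the test where baseline is structurally zero: the rule in 7.4 covers categorical change without exception, the change tables state no filter for trauma or infection, and the conflict between item 14 and Section 6 remains.

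**Conclusion.** The point holds for two groups of variables. For genital ulcers/lesions in all women, and for adverse events, baseline positives are zero by design, and McNemar's test there cannot tell a gel effect from background. The wider genital signs are affected at least in the low-risk half. Other baseline findings may be lowered by the abstinence rule but are not fixed at zero.

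The size depends on a background rate that the protocol does not give: from about nominal at 4% to more likely than not at 10% if all 60 women are clean, and far less if only 30 are. These figures assume an exact two-sided 0.05 test. The damage is confined to secondary change tables; the primary safety tabulation, the sample size reasoning and the suspension rule stand. It is a correction worth making, because the test is invalid for these variables and item 14 contradicts the adverse event definition.

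**What to change.** In 7.4 and Appendix VIII, items 10, 12 and 14:

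1. State that McNemar's test is not applied to findings that are exclusionary at Day 0 or to adverse events.
2. For these, report the number and proportion of women with a new finding, by visit and cumulatively, each woman counted once, with the exact confidence intervals that 7.4 already names (state the level, 95%).
3. Keep paired tests for variables that are free to be present at Day 0, such as asymptomatic BV.
4. In item 14, replace adverse events at baseline with symptoms and findings recorded at Day 0, so that the table agrees with Section 6.

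Tabulating findings by time since last intercourse, from the Daily Study Records, would help interpretation but is optional.

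The cost is wording only: no new data, visits or participants. A few secondary p-values are replaced by intervals.

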#### 7.4.1 Primary Analyses

Primary data analyses will tabulate the number of primary endpoints listed in Section 7.1.1 — observed during the study. All participants who enroll in the study will be included in each tabulation. Individual participants will contribute once to the calculation of event rates. Additional safety analyses will tabulate the number and type of AEs observed overall and by severity and relationship to product. AEs that lead to discontinuation of product use and/or study participation will be tabulated separately. The temporal relationship of product application and AE onset, and the duration of symptoms, also will be evaluated. Finally, baseline and Day 14 laboratory measures will be summarized and the change in function, defined as the difference between the baseline and Day 14 measurements, will be described.

#### 7.4.2 Secondary Analyses

Secondary data analyses will tabulate endpoints listed in Section 7.1.2. Factors relating to acceptability will be tabulated separately for applicator associated factors (e.g., discomfort, design/packaging, disposal), vehicleassociated factors (e.g., consistency/texture, color, odor), and useassociated factors (e.g., ease of use, partner perceptions/considerations, discharge of product, embarrassment, other social costs), based on participants' questionnaire responses. In addition, transcripts from all focus group discussions will be prepared and analyzed qualitatively. Finally, to determine the effects of this short-term regimen of PRO 2000/5 Gel (P) on vaginal microflora, Gram stain scores at the Day 2, Day 7, and Day 14 follow-up visits will be compared with Gram stain scores at enrollment.

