## 3.2.2 Definition for Female Participants at Low Risk for HIV Infection

- In addition to the exclusion criteria specified in Section 3.2.1, Female participants women will not be defined excluded from the study as at low risk for HIV infection participants if they meet any of the following <del>criteria</del> (based on participant knowledge and self-report):
  - Have been diagnosed and/or treated for an STD (other than HIV) or pelvic inflammatory disease in the three months prior to screening.
  - Have a current male sexual partner who was diagnosed or treated for an STD (other than HIV) in the three months prior to screening.
  - Have a current male sexual partner who has injected non-therapeutic drugs in the three months prior to screening.
  - Have signs, as seen on a pelvic exam or colposcopy, consistent with an STD, other genital tract infection – other than bacterial vaginosis (BV) – or trauma.
    - → Vaginitis
    - → Cervicitis
    - → Edema
    - → Erythema
    - → Ecchymosis
    - Petechial hemorrhage
    - → Vulvar or cervicovaginal lesions, ulcers, abrasions
    - Subepithelial hemorrhage and swelling and
    - Laboratory findings indicative of genital tract infection other than asymptomatic BV

Note: Signs of a asymptomatic BV include the presence of white to grey homogeneous discharge, positive whiff test (amine odor) with addition of KOH, pH >4.5, presence of clue cells, decrease in lactobacilli morphotypes, and increase in non-lactobacilli morphotypes. Women with clinical or gram stain evidence of BV and symptoms (discharge, odor, itching) at screening should be treated and re-evaluated for inclusion in the low risk participants. Women without symptoms, but with clinical or gram stain evidence of BV, or asymptomatic yeast colonization, are eligible as low risk participants.

3. Section 3.2.3 renamed Exclusion Criteria for Male Partners of Female Participants

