### 5.2.2 Laboratory Procedures

- Record results of urine pregnancy test.
- Record results of dipstick urinalysis and process urine culture if dipstick positive for UTI.
- Record vaginal pH measurement.
- Examine wet mount by direct microscopy to detect *T. vaginalis*, *C. albicans* infections, and clue cells for BV.
- Conduct LCR for *N. gonorrhoeae* and *C. trachomatis* if symptomatic.
- If ulcerative lesion was observed, conduct dark field microscopy of swab and serology (RPR with confirmation by FTA-ABS or TP/HA) for *T. pallidum* and prepare and ship swabs to the HPTN Central Lab for M-PCR.
- Store unstained dried smear for Gram staining and batch analysis using the Nugent criteria for BV.
- Conduct complete blood count, APTT/PT, liver and renal function tests.
- Prepare plasma samples for determination of study drug levels for batch shipping at the end of the study.
- Archive plasma and serum.

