#### 7.1.2 Secondary Endpoints

Consistent with the secondary study objective to assess the acceptability of, and adherence to, a short term regimen of 0.5% PRO 2000/5 Gel (P), the following endpoints will be assessed:

• The proportion of participants who were "adherent" to the product use regimen, as defined in Section 4.5.

• The proportion of participants who at their Day 14 Follow-up Visits report via questionnaire that they would be "completely unwilling" to use 0.5% PRO 2000/5 Gel (P) during sexual intercourse in the future.

Consistent with the secondary study objective to evaluate aspects of product acceptability, the following endpoints will be assessed (via questionnaire and focus group discussions):

- Reported positive aspects of using PRO 2000/5 Gel (P).
- Reported negative aspects of using PRO 2000/5 Gel (P).

Consistent with the secondary study objective to assess the feasibility of this population for enrollment in future PhaseII/III vaginal microbicide studies, the following endpoint will be assessed:

• The proportion of participants who at their Day 14 Follow-up Visit report via questionnaire they would be willing to participate in future phase II/III vaginal microbicide trials.

Consistent with the secondary study objective to assess the effect of a twice daily short-term regimen of 0.5% PRO 2000/5 Gel (P) on the vaginal microflora of sexually active HIV-uninfected women in Pune, India, the following endpoint will be assessed:

• The Gram stain scores at enrollment, and follow-up (Days 2, 7 and 14).

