#### Vaginitis:

- For trichomonas or symptomatic BV, treat or refer for treatment. Do not resume product use.
- For symptomatic Candida vaginitis: manage with oral medication and re-evaluate in 3-5 days. If resolved, restart product use. If observed at Day 14, treat and follow up to document resolution.
- For asymptomatic Candida vaginitis :
  - If a participant has asymptomatic Candida vaginitis at the Day 7 Visit she should continue product use and be re-evaluated at the Day 14 Visit
  - If at the Day 14 Visit there are signs and symptoms compatible with vaginitis, treat and follow-up to document resolution.

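### The Gram stain comparison with enrollment tests net change only, so resolving or treated bacterial vaginosis (BV) can offset new BV, mainly at Day 14

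*Protocol*

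**What the plan says.** All references are to the Protocol.

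- **Endpoint.** Section 7.1.2 lists the scores themselves: "The Gram stain scores at enrollment, and follow-up (Days 2, 7 and 14". It defines no count of new BV.
- **Scoring.** Section 5.2.2, like the other laboratory sections: "Store unstained dried smear for Gram staining and batch analysis using the Nugent criteria for BV".
- **Comparison.** Section 7.4.2: "Gram stain scores at the Day 2, Day 7, and Day 14 follow-up visits will be compared with Gram stain scores at enrollment". It names no test.
- **General rule for change.** Section 7.4: "Changes from baseline to follow-up will be analyzed using McNemar's test (for categorical response variables) or the paired t-test (for continuous response variables".
- **Analysis set.** Section 7.4: "all analyses will include available data on all 60 study participants".
- **BV at entry.** Section 3.2.2, in version 2.0 and as amended in November 2003, accepts as low risk participants "Women without symptoms, but with clinical or gram stain evidence of BV". The exclusions for all women in Section 3.2.1 do not list BV.
- **BV on study.** Appendix III: "For trichomonas or symptomatic BV, treat or refer for treatment. Do not resume product use". Section 4.6 still asks for the Day 7 and Day 14 evaluations after product is stopped.

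Appendix VIII lists 19 analysis tables, and none names Gram stain or flora.

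**The concern.** The women start from two different states. A woman with BV at Day 0 can mainly improve, and a woman without it can mainly worsen. A mean change, or a McNemar comparison of gains with losses, subtracts one movement from the other and reports the remainder. Of the women who worsen, those with symptoms are treated, and their later smears then show the result of treatment off product. Nothing in 7.4 or 7.4.2 separates women by flora status at Day 0, counts new BV, or says how post-treatment scores are used.

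At stake is how a finding of no change in flora would be read. Section 1.3 presents this study as a step towards a Phase II/III trial planned in thousands of women. A null net change could be carried forward as evidence that normal flora is preserved, when the test did not look at that question separately.

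**Working it through.** **The plan's own figures.** Section 7.2 gives none for this comparison. Its table concerns two or more toxicity outcomes among 60 women, and it reproduces. At a true rate of 5%, 1 − 0.95^60 − 60 × 0.05 × 0.95^59 = 0.808, against .81 stated.

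**Constructed example.** N = 60 is from the protocol. The rest is assumed, because the protocol gives no BV rates and no score range: 45 women score 2 at Day 0 (no BV) and 15 score 8 (BV). Five of the 45 rise to 7 (+5 each). A resolving woman falls from 8 to 3 (−5). Formula: t = mean change ÷ (SD ÷ √60), 59 degrees of freedom.

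1. No resolution: mean = 25/60 = +0.42, p = 0.024.
2. One woman resolves: mean = (25 − 5)/60 = +0.33, p = 0.10.
3. Five resolve: mean = (25 − 25)/60 = 0.00, p = 1.00. McNemar, 5 against 5: p = 1.00.
4. Five resolve, and all five new cases are treated and back at 2 by Day 14. Mean = −25/60 = −0.42. The sum of squares about the mean is 5 × 25 − 60 × 0.417² = 114.6, so SD = √(114.6/59) = 1.39, t = −0.417/(1.39/√60) = −2.32 and p = 0.024. McNemar, 0 against 5: p = 2 × 0.5^5 = 0.0625.

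New BV at any visit is 5/45 = 11% (exact 95% CI 3.7% to 24.1%) in all four cases.

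**Do the obvious repairs work?**

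- A signed-rank test in case 3 sees five rises and five falls of equal size: exact p = 1.00. It deals with the ordinal scale, not with the cancellation.
- Dropping the treated women in case 4 leaves five falls among 55: mean = −25/55 = −0.45, still an apparent improvement.
- Carrying forward the pre-treatment score of 7 in case 4 restores case 3: mean 0.00. The apparent benefit goes, but the offset by resolution stays. That part needs new BV and resolution reported separately.

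**Sensitivity to the assumed rates.** 1,500 simulated studies of 60 women per row. Assumed: new BV +6, resolved BV −6, treated new BV back to baseline, noise SD 1 per score, two-sided 0.05. New BV is 25% of women without BV at Day 0.

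| BV at Day 0 | Resolved | New cases treated | Mean change | Significant rise (t-test) | Significant fall (t-test) |
|---|---|---|---|---|---|
| 30% | 0 | 0 | 1.06 | 0.895 | 0.000 |
| 30% | 30% | 0 | 0.51 | 0.205 | 0.001 |
| 30% | 30% | half | −0.02 | 0.015 | 0.029 |
| 40% | 50% | half | −0.75 | 0.000 | 0.399 |
| 10% | 0 | 0 | 1.35 | 0.977 | 0.000 |
| 10% | 30% | 0 | 1.18 | 0.837 | 0.000 |
| 10% | 30% | half | 0.49 | 0.287 | 0.001 |

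McNemar on BV yes/no follows the same pattern: 0.968, 0.175 and 0.005 for a significant rise in the first three rows. With 10% BV at Day 0, resolution costs little (0.977 to 0.837). The loss from treated cases does not need BV at Day 0, but it reaches only smears taken after treatment.

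**The case against.** Several points against the concern are sound.

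- **The test is not assigned.** A reader might infer that the protocol prescribes a paired t-test for the Gram stain score, or an analysis in three categories. It does neither. The t-test follows only if the score is treated as continuous. This does not remove the point, because McNemar on BV status cancels in the same way.
- **It could be left to the SAP.** The choice of test and strata often is. Here, however, the protocol itself fixes the endpoint as the score, the two tests for change, and the analysis set.
- **Net change is a legitimate question.** The objective is the effect on flora. In one arm, five women moving up and five down may be natural fluctuation under an inert gel. A reader might infer from the example that harm has been hidden; it does not show that. New BV without a comparator could equally suggest harm where there is none. This stands, and it is why resolution must appear beside new BV.
- **Case 4 is extreme.** Every new case must be symptomatic, found early, treated and recovered by Day 14, and McNemar then gives 0.0625. The smear at the diagnosing visit still counts at that visit.
- **Other tables help.** Symptomatic BV should appear among adverse events and discontinuations (7.4.1). Asymptomatic new BV might not.
- **The direction is not fixed.** A reader might infer that the comparison always leans towards no effect. BV treated at screening can recur, which would push scores up.

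**Conclusion.** The point holds in a limited form. Followed as written, the Gram stain comparison measures net change, and its Day 14 part includes treatment-corrected scores from women taken off product. Resolution and treatment can then offset new BV. Under the assumed rates the effect ranges from slight (chance of a significant rise 0.977 to 0.837) to nearly complete (0.895 to 0.015), and in the most adverse row shown an apparent benefit is significant in 0.399 of studies. These figures rest on assumed BV prevalence, incidence, resolution and treatment, so they show what could happen and do not predict it. The documents do not support saying that a harmful effect will be hidden or will look like a benefit. Only a secondary endpoint is affected; the primary safety tabulation is not.

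**What to change.** In 7.4.2, keep the comparison with enrollment and add:

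1. The proportion with new BV by the Nugent criteria at any follow-up visit among women without BV at Day 0, with an exact 95% CI. Women treated for BV on study count as events.
2. Next to it, the proportion with resolution among women with BV at Day 0.
3. In the comparison with enrollment, for women treated for BV on study, the last pre-treatment score carried forward in place of post-treatment scores. These women are not dropped.

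A signed-rank test for the score is optional and does not replace these items. State that, with one arm, none of these results attributes a change in flora to the gel.

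Cost: analysis wording only, using smears already collected, with no change to clinical management. The downside is a smaller denominator for new BV (45 instead of 60 in the example) and so a wider interval.
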